Philips Mammography Solutions Sweden	Clinical Investigation Plan Comparison of the Philips MicroDose Tomosynthesis System to 2D Digital Mammography	DOC-MTIN-9RWH8K- 8.0 Page 5 of 38
---	---	---

8. DEVICE ACCOUNTABILITY	32
9. INFORMED CONSENT PROCESS	32
10. ADVERSE EVENT REPORTING	33
10.1. Complaint.....	33
10.2. Reporting	34
10.3. Anticipated and unavoidable adverse device effects	34
11. EARLY TERMINATION OR SUSPENSION OF THE RESEARCH	34
12. PUBLICATION POLICY	35
13. REFERENCES	35
APPENDIX I: LIST OF INVESTIGATORS AND SITES	37
APPENDIX II: LIST OF MONITOR(S)/CLINICAL SCIENTIST.....	38

Philips Mammography Solutions Sweden	Clinical Investigation Plan Comparison of the Philips MicroDose Tomosynthesis System to 2D Digital Mammography	DOC-MTIN-9RWH8K- 8.0 Page 6 of 38
---	---	---

SUMMARY

Study Title (ID)	Comparison of the Philips MicroDose Tomosynthesis to 2D Digital Mammography
Subjects	
Approximately 800 women who fulfill all inclusion and exclusion criteria will be enrolled in chronological order from up to 3 different US sites with one study investigator for each site. Two cohorts of patients will be enrolled (i.e., Biopsy and Screening Cohorts). Paired sets of a standard 4-view exam will be collected both from Philips Tomosynthesis system (Tomosynthesis and synthetic 2D images) and a FDA-cleared FFDM system. All enrolled cases will be quality controlled for completeness of image and patient information. Inclusion criteria:
 
 • Female and at least 40 years of age • No contraindication for routine bilateral mammography 
Screening Cohort
 
 • Patient presents for a routine screening mammogram 
Biopsy Cohort
 
 • Patient is scheduled for a biopsy • Patient has a screening detected abnormality 
The reading portion of the study will include approximately 300 normal cases (including some cases determined to be normal after call back after screening mammography), 65 cancer cases, and 40 biopsy proven benign cases.
 
The primary objective of the study is to compare the safety and clinical performance of the Philips MicroDose Tomosynthesis system (Tomosynthesis and synthetic 2D) images to conventional 2D mammography images (FFDM).

Study Design	
The study will be performed in two phases: Image Accrual and Image Reading. Image accrual will be performed in a multicenter setting. Image reading will be designed as a multi-case, multi-reader (MCMR) study with paired image acquisition and reader evaluation. Approximately 18 American Board of Radiology (ABR) certified, and Mammography Quality Safety Act (MQSA) qualified radiologists will review and score the cases.
 
Outcome of the reader study for the two imaging groups will be compared using ROC methodology.

Treatment Groups	
 • Investigational Device: Philips MicroDose Tomosynthesis system (Tomosynthesis prototype Philips MicroDose SI S0) • Comparator: Digital mammography system (2D FFDM)
Primary Objectives	
The primary objective of the study is to compare the safety and clinical performance of the Philips MicroDose Tomosynthesis system (tomosynthesis and synthetic 2D) images and 2D digital mammography (from any FDA cleared FFDM system) images.

Philips Mammography Solutions Sweden	Clinical Investigation Plan Comparison of the Philips MicroDose Tomosynthesis System to 2D Digital Mammography	DOC-MTIN-9RWH8K- 8.0 Page 7 of 38
---	---	---

	Clinical performance will be based on the Area under the Receiver Operating Characteristics curve (ROC AUC). The ROC curves will be generated using a confidence scores (CS) using a numeric scale. The ROC curves will be calculated for each reader.
Secondary Objectives	
The secondary objectives are:
 
 • To compare the average glandular dose for exams performed with Philips MicroDose Tomosynthesis system and the 2D mammography system (2D FFDM). • To compare the non-cancer recall rate for Philips MicroDose Tomosynthesis system and 2D mammography exams. • To compare the sensitivity and specificity of the Philips MicroDose Tomosynthesis system (tomosynthesis and synthetic 2D) to that obtained with a 2D mammography system (2D FFDM). 
The average glandular dose (AGD) will be recorded per subject for each breast (right and left) and view (CC and MLO). Sensitivity will be estimated for each reader as the proportion of cancer cases with per-case BI-RADS category 4 or higher. Specificity will also be estimated by reader as the proportion of non-cancer cases with per-case BI-RADS category less than 4. Cancer determination will be based on biopsy results or the outcome of the one-year follow-up exam.

Supplementary Objectives	
The following supplementary objectives will be evaluated:
 
 • The effect of breast density on AUC for images obtained using the Philips MicroDose Tomosynthesis system and 2D mammography system (2D FFDM). Breast density will be stratified as fatty (i.e., BI-RADS breast density type A and B) and dense (BI-RADS breast density type C and D). • To compare the average image interpretation time for exams performed with Philips MicroDose Tomosynthesis and 2D mammography system (2D FFDM).

1. STATEMENT OF COMPLIANCE

This clinical research shall be conducted in accordance with the Clinical Investigation Plan, and with the ethical principles that have their origin in the Declaration of Helsinki and all applicable regional and/or national regulations. Furthermore, all investigators will complete financial disclosures, as outlined in the 21 CFR part 54. Investigators located in the US shall follow the 21 CFR parts 50, 56 and 812.

This clinical research shall not be started prior to obtaining a favorable opinion from an Ethics Committee (EC)/Institutional Review Board (IRB) and Regulatory authority/Food and Drug Administration (FDA), if required. Any additional requirements imposed by the EC/IRB and/or regulatory authority/FDA shall be followed. Insurance shall be provided for the subjects participating in this clinical trial according to local law.

Philips Mammography Solutions Sweden	Clinical Investigation Plan Comparison of the Philips MicroDose Tomosynthesis System to 2D Digital Mammography	DOC-MTIN-9RWH8K- 8.0 Page 8 of 38
---	---	---

2. ABBREVIATIONS USED

Abbreviations	Explanation of abbreviation
ABR	American Board of Radiology
ACR	American College of Radiology
AGD	Average Glandular Dose measured in [mGy]
AUC	Area Under the Curve
BI-RADS	Breast Imaging- Reporting and Data System
CC	Craniocaudal
CI	Confidence Interval
CRF	Case Report Form
CRA	Clinical Research Associate
CS	Confidence Score
DBT	Digital Breast Tomosynthesis
DF	Degree of Freedom
EC	Ethics Committee
EUREF	European Reference Organisation for Quality Assured Breast Screening and Diagnostic Services
FDA	Food and Drug Administration
FFDM	Full Field Digital Mammography (all U.S. marketed FFDM units incl. MicroDose SI L50)
FOM	Figure-of-Merit
FROC	Free Receiver Operating Characteristics
IFU	Instructions for Use
IRB	Institutional Review Board
MLO	Medio-lateral oblique
MQSA	Mammography Quality Standards Act
MRMC	Multi-Reader, Multi-Case
NI	Non-inferiority
Synthetic 2D	A projection image calculated from tomosynthesis data. Does not require additional radiation exposure.
2D, FFDM	Conventional digital mammography
DBT plus synthetic 2D	Only tomosynthesis images are acquired, and a synthetic 2D image is calculated. Both images are read together.
ROC	Receiver Operating Characteristics

Philips Mammography Solutions Sweden	Clinical Investigation Plan Comparison of the Philips MicroDose Tomosynthesis System to 2D Digital Mammography	DOC-MTIN-9RWH8K- 8.0 Page 9 of 38
---	---	---

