3.3.6. Conclusion

The benefit of the study is to enable new technology that potentially could increase early detection and reduce breast cancer mortality. Furthermore the technology is also expected to reduce radiation dose level compared to existing commercially available flat panel systems.

As the subjects enrolled in the study will be imaged both with tomosynthesis and conventional 2D mammography, additional lesions could be detected in the screening patients that would not have been found only with conventional 2D mammography. However a direct benefit of the enrolled subjects is not expected. Possibly a missed cancer on the 2D mammogram could be detected on the tomosynthesis image. Another scenario is that a benign lesion is detected which could require additional imaging or even biopsy. The tomosynthesis images alone will not be used to make a decision to biopsy, but further work-up of such lesions with conventional imaging might indicate the need for biopsy. If a lesion is found on the tomosynthesis images but not detected on 2D, the radiologist at site might want to do additional imaging to assess the lesion. For the majority of the enrolled patients in the study, there will be no direct benefit as of participating in the study, though it is possible that a cancer that is missed on the 2D might be detected.

A risk that the enrolled subjects in the study are taking when participating in the study, is that they will be exposed to additional radiation. The radiation of the investigations device is comparable to Philips MicroDose SI, which is a low dose digital mammography system (approx. 0.8 mGy per view for a standard examination).

Philips Mammography Solutions Sweden	Clinical Investigation Plan Comparison of the Philips MicroDose Tomosynthesis System to 2D Digital Mammography	DOC-MTIN-9RWH8K- 8.0 Page 13 of 38
---	---	--

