5. STUDY DESIGN

5.1. General

The study is a multicenter, multi-case, multi-reader (MCMR) study with paired image acquisition and reader evaluation. The study will be performed in two phases: Imaging Accrual phase and Imaging Reading phase.

Approximately 800 women who fulfill all inclusion and exclusion criteria will be enrolled in chronological order from approximately 3 different US sites with one study investigator for each site. Two cohorts of patients will be enrolled (i.e., Biopsy and Screening Cohorts). Paired sets of a standard 4-view synthetic 2D and tomosynthesis slices exposed on Philips MicroDose Tomosynthesis system and 4-view mammograms on a FDA cleared FFDM system will be collected. All enrolled cases will be quality controlled for completeness of image and patient information.

A subset of the images collected as part of this study will also be used to validate the spectral breast density measurement. This validation is specified in a separate study protocol [9].

Depending on the experience at the sites, each site could also enroll up to 10 additional women to train the technologists on using the system and whose images will be used for training purposes. These cases will not be used in the reader study. In addition to these cases, images for reader training will be available that have been previously collected under another IRB approved protocol.

Approval for the study will be obtained from the ethics committees for all participating centers. All eligible subjects will provide written informed consent prior to entry into the study, which is defined as being imaged on the Philips MicroDose Tomosynthesis system and an FFDM system. Subject enrollment will be monitored by the sponsor at each site. All subjects will be consecutively enrolled.

All subjects interested in participating in the study will be assigned a unique study identification number. At the time of providing informed consent, subjects will be assigned the next number in sequence from the list of study identification numbers. After study enrollment, subjects will be identified solely by their study identification number on the Case Report Forms (CRF). In addition, all subject specific information will be removed from the images prior to them being electronically submitted to the study sponsor and only the subject's study identification number will be provided. Each participating site will maintain a database linking the study number to subject identification.

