6.1.2. Sample Size Justification for Average Glandular Dose

Another secondary objective of this study is to compare the average radiation dose between the Philips MicroDose tomosynthesis system and FFDM systems. Radiation dose will be evaluated based on the subject overall dose received during the examination. For the null hypothesis, no difference in radiation dose delivered to the patient during a mammographic exam between two systems, will be evaluated.

Using historical data from the study site, the average radiation dose per breast for 20 subjects, 2 sample (MLO + CC) was of 3.6 (standard deviation of 1.1), ranging from 2.4 to 6.7 for the GE FFDM, and of 2.6 (standard deviation of 0.7) ranging from 1.6 to 4.0 for Hologic mammography system. Also, in a previous study, comparing the three systems reported radiation dose per breast of 1.86, 2.91, and 3.03, for Philips MicroDose, Hologic and GE, respectively representing a reduction of radiation of approximately 40% for MicroDose compared to Hologic and or the GE mammography system.

Assuming that the standard deviation for the difference in radiation dose will be approximately 1.5mGy, a sample size of approximately 100 subjects will allow for greater than 80% power to detect a difference in radiation between the two systems of approximately 0.5mGy (i.e., 10% of the overall patient radiation) using a paired t-test with a 0.025 one-sided significance level.

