6.8. Secondary Efficacy Analysis

The secondary objectives are:

- To compare the average glandular dose for exams acquired on Philips MicroDose Tomosynthesis system and the 2D mammography system.
- To compare the non-cancer recall rate for Philips MicroDose Tomosynthesis system and 2D mammography exams.
- To compare the sensitivity and specificity of the Philips MicroDose tomosynthesis system (i.e., Tomosynthesis and synthetic 2D) to that obtained with 2D mammography.

Secondary objectives will only be tested if the null hypothesis for the primary endpoint is rejected. Four secondary endpoints will be evaluated. To control the Type I error, the following pre-specified order using a gatekeeper procedure as described by Dmitrienko et al. (2007) will be used:

Family	Endpoint	Procedure
F1	AUC ROC	Test at the 0.05 level, no adjustment to the p-value
F2	Radiation Dose	Test only if Ho for AUC ROC is rejected, p-value adjusted using HOLM procedure
	Recall Rate	Test only if Ho for AUC ROC is rejected, p-value adjusted using HOLM procedure
F2	Sensitivity	Test only if any Ho for F2 is rejected, p-value adjusted using HOLM procedure
	Specificity	Test only if any Ho F2 is rejected, p-value adjusted using HOLM procedure

The average glandular dose (i.e., radiation dose) refers to the total radiation dose during the exam and is expressed in mGy. The goal is to compare total radiation dose between the Philips MicroDose tomosynthesis system and the FFDM systems. The following hypothesis will be tested:

The average glandular dose (AGD) will be recorded per subject for each breast (right and left) and view (CC and MLO). The following hypothesis will be evaluated:

- Null Hypothesis: $H_0: \mu_2 - \mu_1 > \delta$
- Alternative Hypothesis: $\mu_2 - \mu_1 \leq \delta$

where μ_1 and μ_2 are the mean average glandular dose (i.e., radiation dose) for the Philips MicroDose Tomosynthesis system and FFDM system, respectively, and δ is 10% of the FFDM radiation dose.

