Analysis will be performed using an appropriate analysis of variance. If the required assumptions for the ANOVA are violated, transformation of the data or non-parametric procedures may be used. The 95% confidence interval for the mean difference in radiation dose between the two systems will be constructed. Under this proposal Philips tomosynthesis will be declared as emitting less radiation than the FFDM if the upper bound of the 95% confidence interval for the difference in radiation dose is less than 10% of the FFDM.

The non-cancer recall rate will be recorded per subject. All negative screening, recalled and benign biopsy cases will be included. The following hypothesis will be evaluated:

- Null Hypothesis: $H_0: \pi_2 - \pi_1 = 0$
- Alternative Hypothesis: $\pi_2 - \pi_1 \neq 0$

where π_1 and π_2 are the non-cancer recall rate for the Philips MicroDose Tomosynthesis system and FFDM system, respectively.

Recall rate will be analyzed using the concept of clustered binary data as described by Zhou et al (2011). In this case, each Reader will be considered as multiple observations within the same subject (cluster). The 95% confidence interval for the difference in recall rate will be constructed. If the upper limit to the one-sided 95% Confidence Interval for the difference (Philips minus FFDM) in recall rates among non-cancers is less than 0.05 (delta of 5%), Philips tomosynthesis will be considered as resulting in a similar recall rate to that of 2D FFDM. In addition, a bootstrapping method with replacement will be used to compare average recall rates among all Readers.

The sensitivity or specificity within a reader between the two systems will be estimated, and tested for statistical significance using binomial test for paired data. Results will be summarized across readers using the ANOVA model of Obuchowski and Rockette [11], which applies to any metric of diagnostic accuracy under general conditions. The following hypothesis will be evaluated:

- Null Hypothesis: $H_0: S_2 - S_1 \geq 0.10$

Philips Mammography Solutions Sweden	Clinical Investigation Plan Comparison of the Philips MicroDose Tomosynthesis System to 2D Digital Mammography	DOC-MTIN-9RWH8K- 8.0 Page 31 of 38
---	---	--

- Alternative Hypothesis: $S_2 - S_1 < 0.10$

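### The dose test pools every cleared FFDM model, with the low-dose MicroDose SI L50 permitted, against one 10% margin, so the estimated saving depends on the sites' equipment mix as well as on the device

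*Combined protocol and SAP*

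**What the plan says.** The Summary describes the comparator as "2D digital mammography (from any FDA cleared FFDM system) images", and section 2 spells this out as "Full Field Digital Mammography (all U.S. marketed FFDM units incl. MicroDose SI L50". Women are "enrolled in chronological order from approximately 3 different US sites".

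Sections 4.2 and 6.8 set one FFDM mean against one Philips mean, where "δ is 10% of the FFDM radiation dose". On method, section 6.8 says "Analysis will be performed using an appropriate analysis of variance", with transformation or non-parametric methods as a fallback. It names no term for FFDM model or site and no per-model report. The 60% cap in section 5.1 concerns how women were originally screened, not which FFDM unit was used.

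The plan expects models to differ in dose. Section 3.3.6 says "the technology is also expected to reduce radiation dose level compared to existing commercially available flat panel systems". It also calls the device's radiation comparable to MicroDose SI, "which is a low dose digital mammography system (approx. 0.8 mGy per view for a standard examination"). Section 6.1.2 cites a three-system study with 1.86, 2.91 and 3.03 per breast for MicroDose, Hologic and GE. Its 20-subject site data give a mean of 3.6 "ranging from 2.4 to 6.7 for the GE FFDM, and of 2.6 (standard deviation of 0.7) ranging from 1.6 to 4.0 for Hologic mammography system".

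**The concern.** A single mean and a single relative margin suit a comparator whose members deliver similar doses. Here the permitted comparators differ by far more than the margin, and one of them is the marketed system on which the investigational device is based (section 3.3.3). On the plan's own expectation, a woman imaged on an L50 shows about no saving and a woman imaged on a flat-panel unit shows a large one.

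With about three sites, one site's equipment could make up roughly a third of the data. The pooled figure is then a weighted average whose weights come from procurement. It could hide a model against which Philips gives more dose. The spread between models would also inflate the standard error, because nothing in the stated analysis removes it.

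**Working it through.** **The plan's own sample size.** Inputs from 6.1.2: difference 0.5 mGy, SD of the paired difference 1.5 mGy, one-sided 0.025. n = (1.5 × (1.960 + 0.842) / 0.5)² = 71 by the normal approximation, or 73 with the t distribution. At N=100 power is 91.0%. The stated figure of more than 80% is reproduced.

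**Spread between models.** From the three-system study, 1 - 1.86/2.91 = 36% and 1 - 1.86/3.03 = 39%. Doubling the per-breast values gives exam totals:

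| FFDM model | Exam, mGy | 10% margin, mGy | Power at N=100, true doses equal |
|---|---|---|---|
| MicroDose | 3.72 | 0.372 | 69% |
| Hologic | 5.82 | 0.582 | 97% |
| GE | 6.06 | 0.606 | 98% |

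The planned 0.5 mGy is 10% of about 5 mGy. That is close to an equal three-way mix, (3.72 + 5.82 + 6.06)/3 = 5.2, but not to MicroDose alone.

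**Three readings of the rule.** Section 6.8 does not define the direction of the difference in its confidence-interval rule, so three readings were tried:
- A: Philips minus FFDM, upper bound below +10%.
- B: the hypotheses as written, FFDM minus Philips, upper bound below 10%.
- C: FFDM minus Philips, lower bound above 10%. The plan does not state this; it is the strictest test of a lower-dose claim.

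For an L50 share p, the FFDM mean is F = 3.72p + 5.94(1 - p), where 5.94 averages Hologic and GE. The SD is √(1.5² + p(1 - p) × 2.22²). With the Philips exam at 3.72 mGy, power at N=100 is:

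| L50 share | A | B | C |
|---|---|---|---|
| 0 | >99.9% | about 0% | 100% |
| 1/3 | >99.9% | about 0% | 99.9% |
| 2/3 | >99.9% | about 0% | 36% |
| 1 | 70% | 70% | 0% |

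**When the mix decides reading A.** The rule's expected result changes between an all-L50 and an all-flat-panel comparator only if the Philips dose per breast lies between 1.10 × 1.86 = 2.05 and 1.10 × 2.91 = 3.20 (Hologic) or 1.10 × 3.03 = 3.33 (GE). That is 1.10 to 1.72-1.79 times MicroDose. Setting F = P/1.10 gives the L50 share at which the result flips: 85% at 1.2 times MicroDose, 70% at 1.3 times and 39% at 1.5 times. At 1.3 times (4.84 mGy), moving from one third to two thirds L50 cuts power at N=100 from 99.8% to 5.7%.

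**What pooling can hide under A.** Take an assumed Philips exam of 4.5 mGy and equal thirds of the three models.
- By model: 4.5/3.72 = 1.21, 4.5/5.82 = 0.77 and 4.5/6.06 = 0.74, that is +21%, -23% and -26%.
- Pooled difference: 4.5 - 5.2 = -0.7 mGy.
- Between-model variance: (1.48² + 0.62² + 0.86²)/3 = 1.10. SD = √(2.25 + 1.10) = 1.83.
- Upper limit at N=100: -0.7 + 1.96 × 1.83/10 = -0.34 mGy, against a margin of +0.52.

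A lower dose is declared, yet one stratum is 21% higher. With model as a factor the residual SD is 1.5, and the upper limit at the same mix is -0.7 + 1.96 × 1.5/10 = -0.41.

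**The case against.** A reader might infer that the verdict depends on the equipment mix rather than on the device. The documents do not support that. At the dose section 3.3.6 expects, reading A is expected to pass at every mix, and at N=405 its power is 99.9% even if all comparators are L50. Both the device and the mix matter.

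A reader might also set 3.72 mGy (2 × 1.86) against 3.2 mGy (4 × 0.8) and infer that Philips exceeds the L50 by 16%. That compares two source figures for MicroDose systems; like for like the expected difference is 0%. Nor is a large Hologic-GE conflict established. It appears with the 20-subject site means (2.6 and 3.6), but the three-system study puts those two only 4% apart.

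Other points for the plan stand. The L50 is permitted, but nothing says a site has one, and the site data in 6.1.2 are GE and Hologic. Pairing removes differences between women, though not between FFDM models. The planned ANOVA could accommodate a model factor.

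Excluding L50 women from the confirmatory test is tempting, but it would remove the comparator with no expected saving. That favours the sponsor and gives dose a different comparator from AUC.

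Finally, a lower-dose declaration when Philips gives slightly more can arise with a single FFDM model. That comes from the wording of the rule, not from pooling, and needs its own correction.

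**Conclusion.** The concern holds in this form: one pooled mean and margin, with no pre-specified model or site term, make the size and precision of the dose result depend on equipment mix as well as on the device. The verdict itself is at risk in two situations: under reading A, if the true dose is about 1.10 to 1.7-1.8 times MicroDose; and at the expected dose, under readings B or C once L50 use is extensive enough.

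The size rests on these assumptions: the three-system figures are in mGy and represent the models used; per-breast values double to an exam; the MicroDose figure stands for the L50; the SD of 1.5 mGy applies within each model; and the L50 shares and the 4.5 mGy exam are illustrative. The N for the dose analysis is not stated in 6.8.

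Dose is a gatekept secondary endpoint, so the primary AUC conclusion is not affected. This is a low-cost improvement to the analysis, not evidence that the dose comparison will fail.

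**What to change.** In section 6.8:

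1. Replace the unspecified ANOVA with an analysis of each woman's Philips/FFDM exam dose ratio on the log scale, where a 10% excess is a ratio of 1.10. Include FFDM manufacturer/model as a pre-specified factor, or site if models do not vary within site. State how models are weighted in the overall estimate.
2. Report the ratio and 95% CI for each model, with any L50 women shown separately but kept in the overall test.
3. Word the dose conclusion for the models actually used.
4. Define the sign of the difference, and reconcile the no-difference null in 6.1.2 with the hypotheses and confidence-interval rule in 6.8. An upper bound below +10% for Philips minus FFDM supports a claim of not more than 10% higher; it does not support a claim of less.

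The FFDM model must also be recorded for each exam, because section 5.5.3 says only that dose is read from the DICOM header. The cost is analysis wording and one data item. The overall effect becomes a geometric mean ratio instead of a mean difference in mGy, which can still be reported descriptively. No extra subjects are needed for the pooled test, but per-model intervals will be wider, and a model used at one site cannot be separated from that site.
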